## 10.4.3 Analysis of Other Endpoints

• Number and type of other S+N devices that are used with the turbinate reduction adjunct procedure.

## 10.5 SAFETY ANALYSES

All safety endpoints will be summarized using the safety population.

### Adverse Events

The number of subjects reporting: adverse events, serious adverse events, severe adverse events, device-related adverse events, serious device-related adverse events, unanticipated adverse events, and serious unanticipated adverse events will be summarized. In addition, for each adverse event, the following will be summarized: severity, the relationship to the investigational device, outcome and duration of the resolved adverse events and the duration of the adverse events at trial discontinuation.

### **Device deficiencies**

The number of device deficiencies and the number of patients reporting a device deficiency will be summarised.

Additional summaries of safety endpoints, if applicable, will be described in the SAP.

### 10.6 INTERIM ANALYSES

There are no formal interim analyses planned for this study, however Clinical Activity Reports (CAR) may be produced to faciliate the publication of the results for scientific conferences and publications. Additional adhoc analyses may occur as needed (e.g. for abstracts or publications).

## 11. SAMPLE SIZE JUSTIFICATION

The results of a previous clinical study on an earlier generation of the study device found that 92% of subjects had successful fixation of tissue after one week. It is assumed that the study device will perform at least as well as the 92% found previously. The ICH E9 guidance states that power should be greater than or equal to 80%. Therefore based on statistical precision, the recruitment of 36 subjects would provide us with at least 80% probability of obtaining a 2-sided 95% confidence interval, around the estimate proportion of successful fixations of tissue, to within ±11% precision.

With the same assumption of clinical success rate and same precision target, enrolling 36 subjects in ENTACT (Next Generation) will provide probabilities between 78.4% and 90.3% of obtaining the 2-sided 95% confidence interval of the success rate. To allow for a 10% drop out rate, this study will enrol 40 subjects.

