### CONFIDENTIAL AND PROPRIETARY

Study Protocol	% smith&nephew
A prospective, multi-center, single arm PMCF study to evaluate the safety and performance of ENTACT™ (Next Generation) resorbable septal staple system for septoplasty	Number: ENTACT.ENT.PRO.SEP.2019.05
	Version: 2.0, 27Aug2020 Page: Page 24 of 94

devices for the Sainio study. In Sowerby et al., the authors concluded that the septal stapler can be used without an increased morbidity in comparison to suture closure or impact to subjective patient scores.

Tami et al. reported that the first lot of ENTACT Septal Staplers (2009) failed to perform to design specifications and only four total staples from three staplers were implanted in one patient.

Sainio et al. observed haematoma in one patient in the ENTACT Stapler group. Sainio et al. reported that perforation and haematoma, which occurred at a low rate of 1% each in the study, is in agreement with the study conducted by Tami et al. and stated that "ENTACT Septal Stapler is safe to use". The complications reported in the four studies of the ENTACT stapler are performing in-line with alternative devices on the market as discussed in the State of the Art.

Some of the minor complications observed in the literature were edema, inflammation and infection. Sowerby et al. conducted a prospective, randomized clinical study comparing ENTACT Septal Stapler to quilting sutures in patients undergoing septoplasty. Sowerby et al observed mild edema in 2 patients in both the groups at a 3 week follow up. However, the edema resolved in 2 months. In a prospective, case series, mild inflammation was reported at a 1 week follow up in 21% of the patients in whom ENTACT Septal Stapler was used for approximation of mucoperichondrial flaps after septoplasty whereas no inflammation was observed in 79% of the patients. Expected rates of edema or inflammation following septoplasty were not discussed in the four publications identified. Other complications reported in the literature include bleeding, and fever.

Sainio et al. conducted a retrospective comparative study comparing ENTACT Septal Stapler to the non-stapler group where silicone splints, tamponade, or sutures were used during septoplasty. No significant difference in the complication rate was observed between the

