### 8.3 **STUDY ENDPOINTS**

#### 8.3.1 Primary Endpoint

At the 21-day follow-up visit, the clinician will examine the patient's nasal cavity and will confirm:

- Septum wall straight appearance (yes/no);
- Complete coaptation of perichondrial flaps on septum wall (yes/no);
- Absence of significant local tissue reaction at the staple site (yes/no);
- Absence of hematoma swelling at the staple site (yes/no);
- No need for re-intervention at the surgery site (yes/no);

If all the answers to the questions above are "YES" then clinical success will be inferred (if any answer is "NO" then repair failure will be inferred).

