### Table 9.1.1-1: Study Procedures by Visit

#### CONFIDENTIAL AND PROPRIETARY

This document contains information that is confidential and proprietary to Smith + Nephew PLC and Smith + Nephew, Inc. and is intended for use only by Smith + Nephew and its manufacturer. It shall not be reproduced or copied in whole or in part, nor shall the contents be disclosed by any means without prior written permission from Smith + Nephew, nor shall anyone make any use of it that is contrary to the expressed or implied wishes of Smith + Nephew.

Study Protocol	Smith&nephew
A prospective, multi-center, single arm PMCF study to evaluate the safety and performance of ENTACT™ (Next Generation) resorbable septal staple system for septoplasty	Number: ENTACT.ENT.PRO.SEP.2019.05
	Version: 2.0, 27Aug2020 Page: Page 48 of 94

End of Study/Subject		*	*	*	×.
disposition	-				X

\*As needed

Post-operative visits:

- (1) Day 5±2 covers the true "fixation" period for initial healing
- (2) Day 21±7 covers the standard of care for patient follow-up

(3) Day 42±7 covers the clinical follow-up duration associated with the lifetime of the device Notes:

Subjects who have undergone a re-intervention procedure of the implant will be considered terminated from the study from the date of the re-intervention. Study related data will not be collected following the date of the re-intervention.

All concomitant medications/ procedures including any associated with an AE, SAE or SADE will be recorded.

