## 10.4.2 Analysis of Secondary Endpoints

Nasal cavity assessments at day 5 and day 42 will be summarized and presented as count and percentage of each criterion.

Successful staple deployment at the operative visit will be summarized by count and percentage. A 95% exact confidence interval for a single proportion will be presented for successful staple deployment using the Clopper-Pearson method. The number of staples used and whether the stapler misfired will also be presented.

Total operating room time will be calculated and summarized using descriptive statistics and will be presented descriptively by septoplasty only cases as well as septoplasty and turbinate reduction cases.

Intra-operative time to deploy staples to complete septoplasty, calculated as time between start of closure to when the stapler was handed back to the scrub nurse, will be summarized and presented descriptively by septoplasty only cases as well as septoplasty and turbinate reduction cases.

NOSE score will be calculated and summary statistics will be presented by visit. Change in NOSE score from the pre-operative visit to each post-operative visit will also be presented and an ANOVA model will be used to assess statistical significance.

This document contains information that is confidential and proprietary to Smith + Nephew PLC and Smith + Nephew, Inc. and is intended for use only by Smith + Nephew and its manufacturer. It shall not be reproduced or copied in whole or in part, nor shall the contents be disclosed by any means without prior written permission from Smith + Nephew, nor shall anyone make any use of it that is contrary to the expressed or implied wishes of Smith + Nephew.

Study Protocol	% smith&nephew
A prospective, multi-center, single arm PMCF study to evaluate the safety and performance of ENTACT™ (Next Generation) resorbable septal staple system for septoplasty	Number: ENTACT.ENT.PRO.SEP.2019.05
	Version: 2.0, 27Aug2020
	Page: Page 57 of 94

The VAS Pain score will be summarized by visit. Change in VAS Pain score from the preoperative visit to each post-operative visit will also be presented and an ANOVA model will be used to assess statistical significance.

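### The ±11% precision is stated for a one-week fixation rate of 92% that is then reused, without support, as the success rate of the five-item Day-21 composite

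*Combined protocol and SAP*

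**What the plan says.** Section 11, repeated in the synopsis, cites a study of an earlier generation of the stapler in which "92% of subjects had successful fixation of tissue after one week". It continues: "It is assumed that the study device will perform at least as well as the 92% found previously". From this it concludes that 36 subjects give "at least 80% probability of obtaining a 2-sided 95% confidence interval" within ±11% around the proportion of successful fixations. The next paragraph begins "With the same assumption of clinical success rate and same precision target", quotes probabilities of 78.4% to 90.3%, and enrols 40 to allow for 10% dropout.

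Clinical success is a defined term. Section 8.3.1 lists five items for the 21-day visit (straight septum, complete flap coaptation, no significant local tissue reaction, no hematoma swelling, no need for re-intervention) and says: "If all the answers to the questions above are 'YES' then clinical success will be inferred". The window is Day 21±7. Section 10.4.1 analyses this composite with a Clopper-Pearson interval. It counts septum-appearance and re-intervention failures only when they are device-related.

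On the early visit, the notes to Table 9.1.1-1 say "Day 5±2 covers the true" fixation period of initial healing. Section 10.4.2 says: "Nasal cavity assessments at day 5 and day 42 will be summarized and presented as count and percentage of each criterion". The same section names an exact interval for staple deployment.

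**The concern.** The planning rate and the primary endpoint differ in two ways. One is a fixation result at one week; the other is an all-or-nothing composite of five findings at Day 14 to 28. Section 11 moves from one to the other by changing the label, with no argument that the rates should be similar.

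The precision statement is the only basis given for the sample size, so it needs to refer to the primary endpoint. Section 8.3.7 also speaks of a predefined range for the primary outcome's interval, and the only figures in the documents that could supply one are 92% and ±11%. A reader of the report could then set the Day-21 result beside 92%. A lower figure might reflect tissue reaction alone, and a similar figure would not show that fixation matches the earlier generation.

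The early visit does collect something close to one-week fixation, but the analysis text specifies no interval for it.

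**Working it through.** **Inputs.** Section 11: assumed rate 0.92, 36 evaluable, two-sided 95% interval, half-width at most 0.11, target probability 80%, 40 enrolled. Section 10.4.1: planned interval Clopper-Pearson. Section 8.3.1: the composite. The documents give no composite rate at Day 21, so rates below 0.92 are assumptions.

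**Step 1: reproduce the plan's figures.** The probability is the sum of the binomial terms P(X = x; n, p) over all x whose 95% interval has half-width ≤ 0.11.

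Wald half-width = 1.96 × √[p̂(1 − p̂)/n]. At n = 36:
- x = 32: p̂ = 0.889, half-width 0.103, within target.
- x = 31: p̂ = 0.861, half-width 0.113, outside target.

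So the target is met with at most 4 failures (very low success counts also qualify but have negligible probability). At p = 0.92 the terms for 0 to 4 failures are 0.050 + 0.156 + 0.237 + 0.233 + 0.167 = 0.843, which agrees with at least 80%. The same sum gives 0.784 at n = 30 and 0.903 at n = 40. Those are the two ends of the quoted range, so the range describes n = 30 and n = 40 rather than 36; that is a separate matter. Dropout: 36/0.90 = 40. The arithmetic is sound at 0.92 with a Wald interval.

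**Step 2: the planned interval.** At n = 36, Clopper-Pearson for 33 successes is 77.5% to 98.2% (half-width 0.104, within target). For 32 it is 73.9% to 96.9% (half-width 0.115, outside). The target is met with at most 3 failures: 0.050 + 0.156 + 0.237 + 0.233 = 0.675 after rounding.

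**Step 3: vary the assumed composite rate, n = 36.**

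| True composite rate | Wald | Clopper-Pearson |
|---|---|---|
| 0.92 | 84.3% | 67.5% |
| 0.90 | 71.1% | 50.9% |
| 0.85 | 35.5% | 19.1% |

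A fall of two percentage points in the true rate takes the Wald probability below 80%.

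**Step 4: can the documents say which way 92% errs?** At any one visit the composite cannot exceed its coaptation item. That does not cap it at 92%, because the 92% comes from another visit, another device generation and a measure that is never defined. The evidence points both ways:
- *Lower:* tissue reaction and hematoma can fail a subject who has full coaptation. In Section 4.2.2, "mild inflammation was reported at a 1 week follow up in 21% of the patients" in one series (5/24), and Table 4.2.2-1 lists edema in 2 of 8 in another. Both were mild, and only reactions judged significant count.
- *Higher:* the only one-week coaptation figure in the documents is 24/24 (Section 4.2.1), pooled hematoma is 1/153 (Table 4.4.1-1), and the device-related rule removes some failures.

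As an illustration, take the other four items as independent at 99%, 98% or 95% each. Starting from coaptation of 0.92, the product 0.92 × q⁴ is 0.884, 0.849 or 0.749. Starting from 1.00, q⁴ is 0.961, 0.922 or 0.815. Independence is an assumption; if failures cluster in the same subjects, the composite is higher than these products. The direction is not established.

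**Step 5: what a Day-5 interval would show.** At 36 subjects, 33/36 (91.7%) carries 77.5% to 98.2%, and 36/36 carries 90.3% to 100%. A bare percentage hides that width.

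**The case against.** The strongest reply is that 92% is only a planning value. Section 10.4.1 sets no performance goal and no test against 92%; it reports a count, a percentage and an exact interval, which stay valid whatever rate was assumed. This stands. A reader might infer that the study will judge the device against 92% at Day 21, but no such comparison is planned.

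Second, a reader might infer from Section 10.4.2 that Day-5 coaptation will have no confidence interval. That is too strong. Section 10.1 provides for intervals where appropriate, Section 8.3.7 mentions them for outcome summaries, and Section 10 defers detail to a later SAP. What can be said is that no interval is specified for this item, although one is named for staple deployment.

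Third, Day-5 coaptation might be taken as the same quantity as one-week fixation. The documents do not establish this. Successful fixation is never defined, and the one coaptation figure at one week is 100%, not 92%. Table 9.1.1-1 supports Day 5 as the nearest visit and no more.

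Fourth, Section 8.3.2 lists the Day-5 and Day-42 items without defining a composite, so reporting them item by item matches the endpoint as written.

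What the reply leaves untouched is that Section 11 attaches its precision claim to clinical success, and nothing in the documents supports 92% for that endpoint.

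**Conclusion.** The point holds as a gap in justification. The stated probabilities are correct for a true rate of 0.92 and a Wald interval, but that rate belongs to one-week fixation on an earlier generation and is unsupported for the Day-21 composite. At n = 36 the probability of ±11% is 84% at 0.92, 71% at 0.90 and 36% at 0.85 (Wald), or 68%, 51% and 19% with the planned Clopper-Pearson interval. The two lower rates are assumptions chosen to show sensitivity, not predictions.

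It would be tempting to conclude that true composite success must be below 92% and that the study is therefore too small. The documents do not support that: the device-related rule and the 24/24 coaptation result pull one way, tissue reaction and hematoma the other. The primary analysis remains valid; what is unsupported is the precision promised for it.

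**What to change.** In Section 11 and the synopsis:
- Label 92% as a one-week tissue-fixation rate from an earlier generation.
- State the Day-21 composite success rate separately, as an assumption.
- Give the probability of ±11% at n = 36 over a range such as 0.85 to 0.92, for the Clopper-Pearson interval that will be used, with the Wald figures alongside if wanted.

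In Section 10.4.2, or in the SAP due before database lock, add a Clopper-Pearson 95% interval for the Day-5 coaptation item and describe it as the nearest available measure to the one-week figure, not as an equivalent. Exact intervals for the five-item composite at Days 5 and 42 are optional.

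The data are already collected at the scheduled visits, so the cost is wording and a few lines of output. The downside is that the stated precision becomes less favourable.

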#### CONFIDENTIAL AND PROPRIETARY

Study Protocol	> ∕ smith&nephew
A prospective, multi-center, single arm PMCF study to evaluate	Number:
the safety and performance of ENTACT™ (Next Generation) resorbable septal staple system for septoplasty	ENTACT.ENT.PRO.SEP.2019.05
	Version: 2.0, 27Aug2020
	Page: Page 6 of 94

Secondary Objective(s):	The secondary objectives are to generate performance and health
	economics data to support the use of ENTACT (Next Generation)
	resorbable septal staple.
Safety Objective(s):	Assess safety with reported complications, adverse events, adverse
	device effects, unanticipated serious adverse device effects, and
	device deficiencies.
Sample Size:	40 subjects
	The results of a previous clinical study on previous generations of the
	study device found that 92% of subjects had successful fixation of
	tissue after one week. It is assumed that the study device will perform
	at least as well as the 92% found previously. Therefore based on
	statistical precision, the recruitment of 36 subjects would provide with
	at least 80% probability of obtaining a 2-sided 95% confidence
	interval, around the estimate proportion of successful fixations of
	tissue, to within ±11% precision.
	With the same assumption of clinical success rate and same
	precision target, enrolling3636 subjects in ENTACT, Next Generation
	will provide probabilities between 78.4% and 90.3% of obtaining the
	2-sided 95% confidence interval of the success rate. To allow for a
	10% drop out rate, this study will enroll 40 subjects.
Number of Study Sites:	Up to 3 sites
Targeted Global Regions:	United States (US)

Study Protocol	% smith&nephew
A prospective, multi-center, single arm PMCF study to evaluate	Number:
the safety and performance of ENTACT™ (Next Generation)	ENTACT.ENT.PRO.SEP.2019.05
resorbable septal staple system for septoplasty	Version: 2.0, 27Aug2020
	Page: Page 7 of 94

Inclusion Criteria:	The patient will be eligible for the study if he or she meets all of the
	following inclusion criteria at the baseline screening:
	1. Able and willing to give informed consent by voluntarily
	providing written informed consent in accordance with
	governing Institutional Review Board (IRB);
	2. Clinically significant deviation of the nasal septum;
	3. Willing and able to make all required study visits;
	4. Able to read and understand the approved informed consent
	form and patient reported outcome assessments (written and
	oral).

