#### 8.3.6 Subject Attrition

Subject attrition due to reduction in sample size required for precision analysis has been accounted for in the sample size calculation so that the estimate of the Confidence Interval (CI) to be obtained will still be valid through the most efficient use of available subjects.

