### 10.4 EFFICACY ANALYSIS

## **10.4.1 Analysis of Primary Endpoint**

Data will be collected on whether the septum wall appearance and need for re-intervention at the surgery site are due to the device or the procedure. Only those that are device-related will contribute to the primary endpoint analyses, in line with the primary objective of this study. A binary variable will be defined as follows; one if all five of the following criteria are true and 0 if at least one of the criteria is false:

- Septum wall straight appearance
- Complete coaptation of perichondrial flaps on septum wall
- Absence of significant local tissue reaction at the staple site
- Absence of hematoma swelling at the staple site
- No need for re-intervention at the surgery site

Clinical success will be inferred for a patient if their binary variable is 1. Clinical success will be reported as a count and percentage with a 95% CI using Clopper-Pearson Exact methodology. A logistic model will be used to evaluate the adjusted and unadjusted models for the primary outcome variable. The variables considered important and to be included in the final model are age and BMI. All other baseline and medical factors collected at baseline will be evaluated for

This document contains information that is confidential and proprietary to Smith + Nephew PLC and Smith + Nephew, Inc. and is intended for use only by Smith + Nephew and its manufacturer. It shall not be reproduced or copied in whole or in part, nor shall the contents be disclosed by any means without prior written permission from Smith + Nephew, nor shall anyone make any use of it that is contrary to the expressed or implied wishes of Smith + Nephew.

Study Protocol	Smith&nephew
A prospective, multi-center, single arm PMCF study to evaluate the safety and performance of ENTACT ™ (Next Generation) resorbable septal staple system for septoplasty	Number: ENTACT.ENT.PRO.SEP.2019.05
	Version: 2.0, 27Aug2020
	Page: Page 56 of 94

importance in adjusted models and only those statistically significant in an unadjusted model will be considered in the final model.

This analysis will be carried out using the FAS as the primary analysis population and the PP population using for sensitivity analysis.

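### Section 11 gives 36 subjects two incompatible precision probabilities, and the 80% figure is 67.5% under the Clopper-Pearson interval the plan will report

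*Combined protocol and SAP*

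**What the plan says.** Section 11 starts from an earlier study of a previous device generation, in which "92% of subjects had successful fixation of tissue after one week", and assumes the new device does at least as well. From this it concludes that "the recruitment of 36 subjects would provide us with at least 80% probability of obtaining a 2-sided 95% confidence interval" to within ±11%. The next paragraph reads: "With the same assumption of clinical success rate and same precision target, enrolling 36 subjects" in the new device "will provide probabilities between 78.4% and 90.3% of obtaining the 2-sided 95% confidence interval of the success rate". A 10% dropout allowance then takes 36 to 40 enrolled.

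The Sample Size entry in Section 2 (Synopsis) repeats both statements: "at least 80% probability of obtaining a 2-sided 95% confidence" interval within ±11%, and 36 subjects "will provide probabilities between 78.4% and 90.3% of obtaining the" interval.

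Section 11 names no interval method. Section 10.4.1 does, for the primary endpoint: "Clinical success will be reported as a count and percentage with a 95% CI using Clopper-Pearson Exact methodology". Section 8.3.6 says attrition "has been accounted for in the sample size calculation", so 36 is the evaluable number to which the precision claim applies.

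**The concern.** There are three problems, in descending order of weight.

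1. The two probability statements describe the same sample size, rate and precision target. The coverage calculation then has a single answer. A range is not possible, and a range whose lower end is 78.4% contradicts a promise of at least 80%.
2. The precision claim has to refer to the interval that will be reported. Clopper-Pearson intervals are wider than Wald intervals at counts near those expected here, so a probability worked out for Wald overstates what the planned analysis will deliver.
3. The 92% is a one-week tissue-fixation rate. Section 11 goes on to treat it as the clinical success rate, but Section 8.3.1 defines clinical success as a five-part composite at Day 21. The documents do not show whether the composite rate is higher or lower.

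This is the only quantitative justification of the study size. As it stands, a reader cannot tell which probability applies to 36 subjects, and the one stated does not hold for the planned interval.

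**Working it through.** **Inputs.** True rate p = 0.92, n = 36 evaluable, two-sided 95% interval, target ±11% (all Section 11); enrolled 40 after 10% dropout, and 36/0.9 = 40 reproduces; Clopper-Pearson interval (Section 10.4.1).

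**Definition.** Precision is read as half the total interval width, h(x) = (upper − lower)/2 when x of n succeed. The required probability is the sum of the binomial probabilities P(X = x | n, 0.92) over all x with h(x) ≤ 0.11. At these sample sizes that is P(X ≥ k), where k is the smallest qualifying count near the top of the range.

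**Step 1: reproduce the plan's figures with Wald.** Here h(x) = 1.96 × √[p̂(1 − p̂)/n], with p̂ = x/n.

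| n | smallest x meeting 0.11 | h at that x | h at x − 1 | probability |
|---|---|---|---|---|
| 30 | 27 | 0.1074 | 0.1216 | 78.4% |
| 36 | 32 | 0.1027 | 0.1130 | 84.3% |
| 40 | 35 | 0.1025 | 0.1107 | 90.3% |

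The statement of at least 80% at n = 36 is therefore true under Wald. The range 78.4% to 90.3% is exactly Wald at n = 30 and n = 40. Wilson gives 56.5% and 90.3% at those sizes and Jeffreys 78.4% and 96.2%, so of the three only Wald yields both published figures. At n = 36 all three give 84.3%.

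**Step 2: the planned interval, Clopper-Pearson, at n = 36.**
- 33/36: interval 0.7753 to 0.9825, h = 0.1036, meets the target.
- 32/36: interval 0.7394 to 0.9689, h = 0.1147, misses it.

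So k = 33, and P(X ≥ 33) = P(33) + P(34) + P(35) + P(36) = 0.2333 + 0.2368 + 0.1556 + 0.0497 = 0.6754, or **67.5%**.

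**Step 3: other sample sizes, Clopper-Pearson, p = 0.92, h ≤ 0.11.**

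| n | 36 | 37 | 38 | 39 | 40 | 41 | 42 |
|---|---|---|---|---|---|---|---|
| probability | 67.5% | 65.7% | 81.6% | 80.1% | 78.7% | 77.2% | 88.4% |

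The pattern is saw-toothed and stays above 80% only from n = 42. At n = 40, 36/40 has h = 0.1044 and 35/40 has h = 0.1131.

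**Step 4: sensitivity to the assumed rate, Clopper-Pearson, h ≤ 0.11.**

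| true rate | n = 36 | n = 40 |
|---|---|---|
| 0.90 | 50.9% | 62.9% |
| 0.92 | 67.5% | 78.7% |
| 0.93 | 75.7% | 85.5% |
| 0.94 | 83.2% | 91.0% |
| 0.95 | 89.6% | 95.2% |

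The 80% level is reached at a rate of about 93.6% with n = 36 and 92.2% with n = 40.

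**Step 5: the half-width that does deliver 80%.** With h ≤ 0.115, 32/36 qualifies and the n = 36 probability becomes 0.6754 + 0.1674 = 0.8428 (**84.3%**). At n = 40, 35/40 qualifies and the probability is **90.3%**.

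**The case against.** The strongest reply is about rounding. The target is stated to a whole percent, and the count that decides the result, 32/36, has a Clopper-Pearson half-width of 11.47 points, which rounds to 11. Read that way, at least 80% holds under Clopper-Pearson at every n from 36 to 40. This reading is possible, but the plan does not state it. It supports saying 11.5 points outright rather than leaving 11 in place. Half-width is itself the generous reading: if each limit had to lie within 11 points of the estimate, only 36/36 would qualify, with probability 5.0%.

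A second reply is that the 80% is not an arithmetic slip, since Wald gives 84.3%, and that the fault is only a mismatch between planning and analysis methods. That is correct for the 80% figure. It does nothing for the range.

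A third is that performing at least as well as 92% allows a range of rates. Under Clopper-Pearson at n = 36, 78.4% and 90.3% would correspond to true rates of about 93.3% and 95.1%. But the sentence fixes the same assumed rate, and a range starting at 92% would begin at 67.5% (Clopper-Pearson) or 84.3% (Wald), not 78.4%. The superseded version 1.0 text, shown in Section 21.1.4, attached these figures to 30 to 40 subjects. That explains their origin, but the contradiction stands on the current text alone.

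A fourth is that 36 is the worst planned case. That is fair: with less attrition, 38 or 39 evaluable subjects would reach 80%. The full 40 would not.

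Finally, the 92% is already called an assumption. What remains of that point is minor: the text does not say that the endpoint and its timing differ.

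**Conclusion.** The concern holds. Sections 2 and 11 give two incompatible probabilities for the same 36 subjects, and the range belongs to sample sizes of 30 and 40 under Wald. Under the Clopper-Pearson interval of Section 10.4.1, at a true rate of 92% and a half-width of at most 11 points, the probability is 67.5% with 36 evaluable subjects and 78.7% with 40, against a stated minimum of 80%.

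These figures rest on reading precision as half the total interval width, on 11 meaning 11.0 points, and on 92% applying to the Day 21 composite. The last of these cannot be checked from the documents.

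The consequence is limited. The primary endpoint has no hypothesis test and no numerical threshold, the Clopper-Pearson interval is valid whatever its width, and the shortfall is about half a percentage point (11.47 against 11). It should be fixed because it is the sole numerical basis for the study size.

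**What to change.** Keep 40 subjects and the Clopper-Pearson interval. In Sections 2 and 11:

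- Delete the sentence giving 78.4% to 90.3%.
- Name Clopper-Pearson as the interval behind the calculation and define precision as half the interval width.
- State one set of figures. Either: *with 36 evaluable subjects and a true rate of 92%, there is an 84% probability that the half-width of the Clopper-Pearson 95% interval is at most 11.5 percentage points (90% with 40)*. Or keep 11 points and state 67.5% with 36 and 78.7% with 40.
- Say that 92% is a one-week fixation rate, used as an assumption for the Day 21 five-part composite.

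The cost is rewording in two places, with no added subjects and no change to the analysis. The stated precision becomes slightly less favourable. As a protocol amendment, the change needs the approvals described in Section 15.

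Keeping both 11 points and 80% would instead mean re-sizing: 42 evaluable subjects, or 42/0.9 = 46.7, rounded up to 47 enrolled. That is hard to justify for half a point of half-width in a descriptive study.
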